Attachment 5: Hepatitis B Virus (HBV) Screening With HBV DNA Testing

Subjects must undergo screening for hepatitis B virus (HBV). At a minimum, this includes testing for HBsAg (HBV surface antigen), anti-HBs (HBV surface antibody), and anti-HBc total (HBV core antibody total):

- Subjects who test negative for all HBV screening tests (ie, HBsAg-, anti-HBc-, and anti-HBs-) **are eligible** for this study.
- Subjects who test **negative** for surface antigen (HBsAg-) and test **positive** for core antibody (anti-HBc+) **and** surface antibody (anti-HBs+) **are eligible** for this study.
- Subjects who test **positive only** for **surface antibody** (anti-HBs+) **are eligible** for this study.
- Subjects who test **positive** for surface antigen (HBsAg+) **are NOT eligible** for this study, regardless of the results of other hepatitis B tests.
- Subjects who test **positive only** for **core antibody** (anti-HBc+) must undergo further testing for the presence of hepatitis B virus deoxyribonucleic acid (HBV DNA test). If the HBV DNA test is **positive**, the subject **is NOT eligible** for this study. If the HBV DNA test is **negative**, the subject **is eligible** for this study. In the event the HBV DNA test cannot be performed, the subject **is NOT eligible** for this study.

For subjects who **are not eligible for this study due to HBV test results**, consultation with a physician with expertise in the treatment of hepatitis B virus infection is recommended.

Eligibility based on hepatitis B virus test results			
Action	Hepatitis B test result		
	Hepatitis B surface antigen (HBsAg)	Hepatitis B surface antibody (anti-HBs)	Hepatitis B core antibody (anti-HBc total)
Include	—	—	—
	—	+	—
	—	+	+
Exclude	+	— or +	— or +
	—	—	+
Require testing for presence HBV DNA*	—	—	+
* If HBV DNA is detectable, exclude from the clinical study. If HBV DNA testing cannot be performed, or there is evidence of chronic liver disease, exclude from the clinical study.			

Attachment 6: Anticipated Events

Anticipated Event

An anticipated event is an AE (serious or non-serious) that commonly occurs as a consequence of the underlying disease or condition under investigation (disease related) or background regimen.

For the purposes of this study the event of psoriasis will be considered anticipated event.

Reporting of Anticipated Events

All AEs will be recorded in the eCRF regardless of whether considered to be anticipated events and will be reported to the sponsor as described in Section 12.3.1, All Adverse Events. Any anticipated event that meets SAE criteria will be reported to the sponsor as described in Section 12.3.2, Serious Adverse Events. These anticipated events are exempt from expedited reporting as individual single cases to Health Authorities. However, if based on an aggregate review, it is determined that an anticipated event is possibly related to study drug, the sponsor will report these events in an expedited manner.

Anticipated Event Review Committee (ARC)

An Anticipated Event Review Committee (ARC) will be established to perform reviews of pre-specified anticipated events at an aggregate level. The ARC is a safety committee within the sponsor's organization that is independent of the sponsor's study team. The ARC will meet to aid in the recommendation to the sponsor's study team as to whether there is a reasonable possibility that an anticipated event is related to the study drug.

Statistical Analysis

Details of statistical analysis of anticipated events, including the frequency of review and threshold to trigger an aggregate analysis of anticipated events will be provided in a separate Anticipated Events Safety Monitoring Plan (ASMP).

INVESTIGATOR AGREEMENT

CNTO 1959 (guselkumab)

Clinical Protocol CNTO1959PSO3009 Amendment 1

INVESTIGATOR AGREEMENT

I have read this protocol and agree that it contains all necessary details for carrying out this study. I will conduct the study as outlined herein and will complete the study within the time designated.

I will provide copies of the protocol and all pertinent information to all individuals responsible to me who assist in the conduct of this study. I will discuss this material with them to ensure that they are fully informed regarding the study drug, the conduct of the study, and the obligations of confidentiality.

Coordinating Investigator (where required):

Name (typed or printed): _____
Institution and Address: _____

Signature: _____ Date: _____

3. To modify the sensitivity analysis based on multiple imputation (MI) by first imputing intermittent missing data and then using regression method to impute the remaining missing data. In addition, to spell out details about the MI including number of imputations and seeds.
4. To add sensitivity analyses for all the major secondary endpoints.
5. To add the detailed investigator site pooling strategy given the enrollment has completed.

Additionally, minor grammatical, formatting, or spelling changes were made.

ABBREVIATIONS

AE	adverse event
CI	confidence interval
CRF	case report form
CSR	Clinical Study Report
DBL	Database lock
DC	Discontinuation
DMC	Data Monitoring Committee
ECG	Electrocardiogram
eCRF	electronic case report form
eC-SSRS	Electronic Columbia-Suicide Severity Rating Scale
FDA	Food and Drug Administration
IgG1 λ	immunoglobulin G1 lambda
IGA	Investigator's Global Assessment
IWRS	interactive web response system
mAb	monoclonal antibody
MedDRA	Medical Dictionary for Regulatory Activities
NAbs	neutralizing antibodies
NCI-CTCAE	National Cancer Institute-Common Terminology Criteria for Adverse Events
PASI	Psoriasis Area and Severity Index
PK	pharmacokinetic(s)
SAE	serious adverse event
SAP	Statistical Analysis Plan
SD	standard deviation

1. INTRODUCTION

This statistical analysis plan (SAP) contains definitions of analysis sets, derived variables, and statistical methods for the analysis of efficacy, safety and pharmacokinetics for the guselkumab (CNTO 1959) clinical study CNTO1959PSO3009. Guselkumab is a fully human immunoglobulin G1 lambda (IgG1 λ) monoclonal antibody (mAb) that inhibits the biological activity of IL-23 and therefore has the potential for the treatment of psoriasis.

1.1. Trial Objectives

Primary Objectives

The primary objective is to evaluate the efficacy of guselkumab compared with secukinumab for the treatment of subjects with moderate to severe plaque-type psoriasis.

Secondary Objectives

The secondary objectives are to evaluate:

- The safety and tolerability of guselkumab in subjects with moderate to severe plaque-type psoriasis.
- The PK and immunogenicity of guselkumab after subcutaneous (SC) administrations in subjects with moderate to severe plaque-type psoriasis.

1.2. Trial Design

This is a Phase 3, randomized, double-blind, multicenter, active-comparator-controlled study in subjects with moderate to severe plaque-type psoriasis. The target population is adult men or women, with a diagnosis of plaque-type psoriasis (with or without PsA) for at least 6 months before the first administration of study drug. Subjects must have moderate to severe plaque-type psoriasis defined by IGA ≥ 3 , PASI ≥ 12 , and involved body surface area (BSA) $\geq 10\%$. Subjects must be candidates for either systemic therapy or phototherapy for psoriasis, and may have previously received some systemic therapies or phototherapy for psoriasis. Subjects with nonplaque forms of psoriasis (eg, erythrodermic, guttate, or pustular) or with drug-induced psoriasis (eg, a new onset of psoriasis or an exacerbation of psoriasis from beta blockers, calcium channel blockers, or lithium) are excluded. Subjects who have ever received guselkumab or secukinumab are also excluded.

Key features of study drug administration for each treatment group are outlined below.

Week 0 through Week 44 (Blinded Treatment Period)

As depicted in [Figure 1](#), approximately 1,040 subjects who satisfy all inclusion and exclusion criteria will be randomized in a 1:1 ratio to 1 of 2 treatment arms:

- **Group I** (n=520): guselkumab 100 mg SC at Weeks 0, 4, 12, and q8w thereafter through Week 44.
- **Group II** (n=520): secukinumab 300 mg SC at Weeks 0, 1, 2, 3, 4 and q4w thereafter through Week 44.

[figure not shown]
After Week 44 through Week 56 (Follow-up Period)

The follow-up period will begin after Week 44 and extend through Week 56.

There is one database locks (DBL) in this study at Week 56. The Sponsor, the investigators, subjects, and site monitors will be unblinded after the Week 56 DBL has occurred. The end of the study is defined as the timepoint when the last subject completes the Week 56 visit.

A diagram of the study design is provided in [Figure 1](#).

Figure 1: Schematic Overview of the Study

1.3. Statistical Hypotheses for Trial Objectives

The proposed randomized, blinded, two-active-arm trial will evaluate the relative performance of guselkumab and secukinumab utilizing a comprehensive battery of endpoints (eg, PASI 75, 90, and 100) at various timepoints (eg, Week 12 and Week 48) using rigorous statistical methodology to control for multiplicity.

While the ultimate goal of the trial is to demonstrate that the efficacy of guselkumab is superior to secukinumab for PASI 90 at Week 48, initial testing for non-inferiority is included for this endpoint because the overall profile of guselkumab will likely be favorable compared with secukinumab (in terms of potential for increased compliance and lesser patient burden), even if final results only indicate the relative efficacy is no worse for this endpoint.

Primary Hypothesis:

The primary hypotheses are that guselkumab treatment is non-inferior to secukinumab as assessed by the proportion of subjects achieving a PASI 90 response at Week 48 with a noninferiority margin of 10% and, once non-inferiority is established, that guselkumab is superior to secukinumab as assessed by the proportion of subjects achieving a PASI 90 response at Week 48.

Major secondary hypotheses are that guselkumab treatment is:

- Non-inferior to secukinumab for the maintenance of a PASI 75 response as assessed by the proportion of subjects who achieve a PASI 75 response at both Week 12 and Week 48 with a non-inferiority margin of 10% and, once non-inferiority is established, that guselkumab is superior to secukinumab as assessed by the proportion of subjects who achieve a PASI 75 response at both Week 12 and Week 48.
- Non-inferior to secukinumab at Week 12 as assessed by the proportion of subjects who achieve PASI 90 at Week 12 with a non-inferiority margin of 10%.
- Non-inferior to secukinumab at Week 12 as assessed by the proportion of subjects who achieve PASI 75 at Week 12 with a non-inferiority margin of 10%.
- Non-inferior to secukinumab at Week 48 as assessed by the proportion of subjects who achieve PASI 100 at Week 48 with a non-inferiority margin of 10% and, once noninferiority is established, that guselkumab is superior to secukinumab as assessed by the proportion of subjects who achieve a PASI 100 response at Week 48.
- Non-inferior to secukinumab at Week 48 as assessed by the proportion of subjects who achieve an IGA score of cleared (0) at Week 48 with a non-inferiority margin of 10% and, once non-inferiority if established, that guselkumab is superior to secukinumab as assessed by the proportion of subjects who achieve an IGA score of cleared (0) at Week 48.
- Non-inferiority test to secukinumab at Week 48 as assessed by the proportion of subjects who achieve an IGA score of cleared (0) or minimal (1) at Week 48 with a non-inferiority margin of 10% and, once non-inferiority if established, that guselkumab is superior to secukinumab as assessed by the proportion of subjects who achieve an IGA score of cleared (0) or minimal (1) at Week 48.

1.4. Sample Size Justification

This study is designed to evaluate the efficacy of guselkumab 100 mg vs secukinumab 300 mg. The power and sample size were evaluated for the primary endpoint of PASI 90 at Week 48. In addition, since the response rate for guselkumab for PASI 100 at Week 48 is around 50% where the variability is the highest, the power and sample size were also evaluated for this major secondary endpoint. The assumptions for the sample size and power calculations were based on the data from the guselkumab CNTO1959PSO3001 and CNTO1959PSO3002 and the secukinumab Phase 3 studies (ERASURE and FIXTURE).¹ The assumptions used are as follows:

- The proportion of subjects who achieve a PASI 90 response at Week 48 is 70% to 80% in subjects receiving guselkumab and 60% to 70% for subjects receiving secukinumab.
- The proportion of subjects who achieve a PASI 100 response at Week 48 is 44% to 51% in subjects receiving guselkumab and 35% to 40% for subjects receiving secukinumab.

Approximately 1,040 subjects are planned to be randomized in a 1:1 ratio to either guselkumab 100 mg (n=520) (administered at Weeks 0, 4, 12 and q8w thereafter until Week 44) or secukinumab 300 mg (n=520) (administered at Weeks 0, 1, 2, 3, and 4 and q4w thereafter until Week 44).

Based on the above assumptions, the planned sample size, and a noninferiority margin of 10%, the power to demonstrate the non-inferiority for the primary endpoint of PASI 90 at Week 48 and the major secondary endpoint of PASI 100 at Week 48 will be > 99%.

Table 1 provides the power for detecting a treatment difference (superiority of guselkumab over secukinumab) under varying assumptions at a significance level of 0.05 for the primary endpoint PASI 90 at Week 48 and the major secondary endpoint of PASI 100 at Week 48.

Table 1: Power to Detect a Treatment Effect Based on Different Proportions of Subjects Achieving the Primary Endpoint PASI 90 at Week 48 and the Major Secondary Endpoint PASI 100 at Week 48

Secukinumab 300 mg (n=520)	Primary Endpoint PASI 90 at Week 48	
	Guselkumab 100 mg (n=520)	
60%	70%	92%
	75%	>99%
	75%	94%
65%	80%	>99%
	80%	96%
70%	Selected Major Secondary Endpoint PASI 100 at Week 48	
	44%	84%
	45%	91%
	46%	95%
	49%	83%
40%	50%	90%
	51%	95%

PASI = Psoriasis Area and Severity Index.

1.5. Randomization and Blinding

1.5.1. Procedures for Randomization and Stratification

Central randomization will be implemented in this study. Subjects will be randomly assigned to 1 of 2 treatment groups based on a computer-generated randomization schedule prepared before the study under the supervision of the sponsor. The randomization will be balanced by using randomly permuted blocks and will be stratified by study site. The interactive web response system (IWRS) will assign a unique treatment code, which will dictate the treatment assignment and matching study drug kit for the subject. The requestor must use his or her own user

identification and personal identification number when contacting the IWRS, and will then give the relevant subject details to uniquely identify the subject.

1.5.2. Blinding

The investigator will not be provided with randomization codes. The codes will be maintained within the IWRS, which has the functionality to allow the investigator to break the blind for an individual subject.

Data that may potentially unblind the treatment assignment (eg, treatment allocation, study drug preparation/accountability data [including unblinded personnel], and administration of study drug (see details in Section 6 of the protocol) will be handled with special care to ensure that the integrity of the blind is maintained and the potential for bias is minimized. This can include making special provisions, such as segregating the data in question from view by the investigators, clinical team, or others as appropriate until the time of DBL and unblinding.

Under normal circumstances, the blind should not be broken for subjects, investigators, or site monitors until the Week 56 database is locked and finalized. Otherwise, the blind should be broken only if specific emergency treatment/course of action would be dictated by knowing the treatment status of the subject. In such cases, the investigator may in an emergency determine the identity of the treatment by contacting the IWRS. It is recommended that the investigator contact the sponsor or its designee if possible to discuss the particular situation, before breaking the blind. Telephone contact with the sponsor or its designee will be available 24 hours per day, 7 days per week. In the event the blind is broken, the sponsor must be informed as soon as possible. The date and reason for the unblinding must be documented by the IWRS, in the appropriate section of the electronic case report form (eCRF), and in the source document. The documentation received from the IWRS indicating the code break must be retained with the subject's source documents in a secure manner.

Subjects who have had their treatment assignment unblinded should continue to return for scheduled evaluations. The decision to continue or discontinue study treatment for these subjects will be based upon consultation of the investigator with the medical monitor.

2. GENERAL ANALYSIS DEFINITIONS

This analysis plan provides the general analysis definitions and describes the planned subject information, efficacy, safety, pharmacokinetics, and antibody analyses for the two planned DBLs.

2.1. Imputation Rules for Partial or Missing AE Dates

Partial AE onset dates will be imputed as follows:

- If the onset date of an adverse event is missing day only, it will be set to:
 - First day of the month that the AE occurred, if month/year of the onset of AE is different than the month/year of the study agent start

- The day of study agent start, if the month/year of the onset of AE is the same as month/year of the study agent start date and month/year of the AE resolution date is different
- The day of study agent start or day of AE resolution date, whichever is the earliest, if month/year of the onset of AE and month/year of the study agent start date and month/year of the AE resolution date are same
- If the onset date of an adverse event is missing both day and month, it will be set to the earliest of:
 - January 1 of the year of onset, as long as this date is on or after the study agent start date
 - Month and day of the study agent start date, if this date is in the same year that the AE occurred
 - Last day of the year if the year of the AE onset is prior to the year of the study agent start date,
 - The AE resolution date.
- Completely missing onset dates will not be imputed.

Partial AE resolution dates not marked as ongoing will be imputed as follows:

- If the resolution date of an adverse event is missing day only, it will be set to the earliest of the last day of the month of occurrence of resolution or the date of death, if the death occurred in that month.
- If the resolution date of an adverse event is missing both day and month, it will be set to the earliest of December 31 of the year or the day and month of the date of death, if the death occurred in that year.

Completely missing resolution dates will not be imputed.

2.2. Visit Windows

Nominal visits will be used for all by-visit analyses in the study unless otherwise specified, regardless of the scheduled visit window. The study visits scheduled should occur at the times delineated in the Time and Events Schedule of the protocol. From Weeks 0 to 4 it is expected that all subjects will attend visits within a range of ± 3 days. After Week 4 and through Week 44, it is expected that all visits will occur within a range of ± 7 days. Any visits outside of these ranges should be discussed with the sponsor. If a study visit occurs outside the specified visit window, the subject should then resume his or her normal dose schedule relative to the baseline visit (Week 0) as soon as possible. All other follow-up study visits should occur within ± 14 days of the scheduled study visit. Any out-of-range visit should be documented in the subject's source notes.

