
FOOTNOTES:
 
a: The screening visit should occur within approximately 4 weeks before the Week 0 visit.
 
b: All Week 48 study procedures should be performed on any subject who terminates the study prior to Week 48, except for collection of serum for biomarkers. If a subject terminates post-Week 48, sites should make every effort to conduct the Week 56 assessments.
 
c: All study procedures and evaluations should be completed before administration of study drug. Assessments for subjects who discontinue study agent administration or withdraw from the study are discussed in Section 10.2.
 
d: Women of childbearing potential must have a negative urine pregnancy test before randomization, before study drug administration, and at all study visits.
 
e: The eC-SSRS should be completed by the subject before any tests, procedures, or other consultations to prevent influencing subject perceptions,
 
f: A tuberculin skin test is additionally required if the QuantiFERON-TB Gold test is not approved/registered in the country in which this study is being conducted.
 
g: Laboratory tests are listed in Section 9.6.
 
h: Subjects must fast (ie, no food or beverages [except water]) for at least 8 hours before blood is drawn for lipid panel. All other visits can be nonfasting.
 
i: All blood samples must be collected before study agent administration at visits when a study agent administration is scheduled. Details will be provided in the Laboratory Manual.
 
j Serum biomarker measurements will include but are not limited to: serum IL-17A, IL-17F, and IL-22. For subjects who discontinue from the study prior to Week 48, serum is not to be collected for measurement of biomarkers.
 
k Biopsy samples for RNA and tissue histology will be collected only from subjects who consent to participate in the optional biopsy substudy. Biopsy samples will be used to assess the cellular and molecular profiles of psoriatic skin lesions at baseline and during treatment.
 
[REDACTED]
 
m: Blood samples for genetic (DNA) analyses will be collected only from subjects who sign a separate consent form to participate in the genetic (DNA) evaluations.
																		

ABBREVIATIONS

BCG	Bacille Calmette-Guérin
BSA	body surface area
CSR	clinical study report
DBL	database lock
ECG	electrocardiogram
eCRF	electronic case report form
eC-SSRS	electronic Columbia-Suicide Severity Rating Scale
eDC	electronic data capture

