- The subject has a reaction resulting in myalgia and/or arthralgia with fever and/or rash (suggestive of serum sickness and not representative of signs and symptoms of other recognized clinical syndromes) occurring 1 to 14 days after an injection of study drug. These may be accompanied by other events including pruritus, facial, hand, or lip edema, dysphagia, urticaria, sore throat, and/or headache.
- Discontinuation of study treatment should be considered for subjects who report suicidal ideation with intention to act (“4”), suicidal ideation with specific plan and intent (“5”), or a suicide attempt (interrupted suicide attempt, aborted suicide attempt, or preparatory behaviors for making a suicide attempt) on a postbaseline eC SSRS assessment. Discussion of such subjects with the medical monitor or designee is required.
- Discontinuation of study treatment should be considered for subjects who develop a serious or opportunistic infection. Discussion of such subjects with the medical monitor or designee should also be considered.

Subjects who decide to discontinue study drug administration must be interviewed by the investigator to determine if a specific reason for discontinuing study drug can be identified. Subjects should be explicitly asked about the possible contribution of AEs to their decision to discontinue study drug; investigators should confirm that any AE information elicited has been documented. If the subject elects to discontinue study drug due to an AE, the event should be recorded as the reason for study drug discontinuation, even if the investigator’s assessment is that the AE would not require study drug discontinuation. The reason for study drug discontinuation must be documented in the eCRF and in source documents. Study drug assigned to a subject who discontinues may not be assigned to another subject.

If the subject discontinues study treatment before his or her last scheduled injection, he or she should return for the remaining regularly scheduled study visits for at least 12 weeks after receiving the last administration of study drug. For subjects who complete their final study visit prior to Week 48, every effort should be made to conduct the Week 48 assessments as indicated in the Time and Events Schedule. For subjects who discontinue from the study prior to Week 48, serum is not to be collected for measurement of biomarkers.

Withdrawal From the Study

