5.1.3.3. Missing Data Imputation

After the treatment failure rules are applied, the remaining missing data will be handled as follows for all of the efficacy analyses including the analyses at key visits (eg, Week 12 and Week 48) and over time:

- Non-responder imputation will be applied for binary endpoints.
- No imputation will be performed for continuous endpoints and the values will remain as missing.

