5.2.2. Estimand

Population: subjects with moderate-to-severe plaque psoriasis who are randomized and treated with guselkumab 100 mg or secukinumab 300 mg.

Endpoint: the proportion of subjects who achieve a PASI 90 response at Week 48

Measure of Intervention: the effect of the initially randomized treatment regardless of what treatments are actually received. Non-responder status will be assigned if treatment failure criteria are met or data are missing.

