5.2.4. Data Handling

Subjects who meet treatment failure criteria specified in Section 5.1.3.1 prior to Week 48 will be considered PASI 90 nonresponders at Week 48. In addition, subjects with a missing PASI score at Week 48 or who do not return for evaluation at Week 48 will be considered PASI 90 nonresponders at Week 48.

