5.2.5. Sensitivity Analysis

To assess the robustness of the primary endpoint analysis results, the following three sensitivity analyses will be conducted.

Sensitivity Analysis 1

For subjects who have a missing PASI score at Week 48, the score will not be imputed. That is, the analysis will be performed using observed data, after applying treatment failure rules (as defined in Section 5.1.3.2).

Sensitivity Analysis 2

The second sensitivity analysis will be performed by using multiple imputations (MI), after applying treatment failure rules (as defined in Section 5.1.3.2). The intermittent missing PASI scores which include PASI scores at Week 0, Week 4 through Week 48 will be imputed using the Markov Chain Monte Carlo (MCMC) algorithm with 200 imputed data sets and seed = 123 to make the missing data pattern monotone. The PASI 90 responses will then be derived based on the imputed score at or before Week 48. The remaining missing data for the PASI 90 response will be imputed with monotone logistic regression with treatment group, baseline PASI, investigator site and PASI 90 response status starting from Week 4 in the model with one imputed dataset and seed = 789 to fill in the remaining missing items in each of the 200 copies of datasets. If the model fails to converge, investigator site will not be included as an explanatory variable. The proportion difference of PASI 90 response at Week 48 adjusted for investigator site (pooling) using Mantel-Haenszel weight between the guselkumab 100 mg and the secukinumab 300 mg groups and its 95% CI combining multiple datasets will also be provided. In addition, the superiority test of guselkumab to secukinumab combining all the multiple imputation datasets using the CMH chi-square test stratified by investigator site will be performed at a significance level of 0.05.

Sensitivity Analysis 3

A generalized linear model with logit link for binary repeated measurement data will also be performed as a sensitivity analysis to compare the proportion of subjects responding to treatments at Week 48, after applying treatment failure rules (as defined in Section 5.1.3.2). The model will include baseline PASI score, treatment group, investigator site, visit starting from Week 4, the interaction of treatment group and visit, and the interaction of baseline PASI score

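### Could PASI and IGA scores taken at an exit before Week 48 be counted as Week 48 data?

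*SAP*

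**What the plan says.** **What happens at an early exit.** Footnote b of the protocol's Time and Events Schedule says "All Week 48 study procedures should be performed on any subject who terminates the study prior to Week 48", with serum biomarkers excepted. Protocol 10.2 says a subject who stops treatment early "should return for the remaining regularly scheduled study visits for at least 12 weeks after receiving the last administration of study drug". It adds: "For subjects who complete their final study visit prior to Week 48, every effort should be made to conduct the Week 48 assessments". The same section makes a similar request for subjects who withdraw from the study. PASI and IGA are scheduled at every visit from screening to Week 56, and the schedule has no early-termination column.

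**How visits are assigned.** SAP 2.2: "Nominal visits will be used for all by-visit analyses in the study unless otherwise specified, regardless of the scheduled visit window".

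**How absent data are handled.** SAP 5.1.3.3 begins "After the treatment failure rules are applied, the remaining missing data will be handled as follows for all of the efficacy analyses" and then gives nonresponder imputation for binary endpoints. The estimand in SAP 5.2.2 says "Non-responder status will be assigned if treatment failure criteria are met or data are missing". For the primary endpoint, SAP 5.2.4 classes as nonresponders "subjects with a missing PASI score at Week 48 or who do not return for evaluation at Week 48". SAP 5.3.3 sends the major secondary endpoints to 5.1.3, and SAP 5.3.2 applies the primary endpoint's statistical methods to them.

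**The concern.** Read together, these rules leave a hole. A site following footnote b might record the exit assessment on the Week 48 form. The SAP takes nominal labels whatever the timing, so a score obtained weeks earlier would be analysed as Week 48.

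Only SAP 5.2.4 mentions not returning at Week 48, and it covers the primary endpoint alone. The four major secondary endpoints that use Week 48 (PASI 75 at Weeks 12 and 48, PASI 100, IGA 0, IGA 0 or 1) rely on 5.1.3, which acts on treatment failure and missing data. A score filed under Week 48 is not missing.

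The sensitivity analyses that probe missing data would be affected too. Sensitivity Analyses 1 and 3 would treat the exit score as observed. In Sensitivity Analysis 2, where "The intermittent missing PASI scores which include PASI scores at Week 0, Week 4 through Week 48 will be imputed" by MCMC, a dropout would look like a subject with a gap in the middle. At stake would be the meaning of Week 48 in tests that belong to the alpha-controlled sequence.

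**Working it through.** **1. Who could be affected.** Protocol 10.2 asks for at least 12 weeks of scheduled visits after the last administration, so the earliest final visit is the last dose plus 12 weeks.

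| Last dose (week) | Earliest final visit (week) | Weeks before Week 48 |
|---|---|---|
| 0 | 12 | 36 |
| 16 | 28 | 20 |
| 32 | 44 | 4 |
| 36 | 48 | 0 |

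Subjects dosed at Week 32 or earlier can therefore finish before Week 48. From Week 4 on, doses are four weeks apart, and each dose week plus 12 is itself a scheduled visit. A last dose at Week 1, 2 or 3 gives Week 13, 14 or 15, so the first scheduled visit that satisfies the rule is Week 16. In all these cases the final visit already has a nominal week, and PASI and IGA are due there anyway. Under SAP 2.2 a final visit at Week 28 is Week 28, and Week 48 is missing.

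Two other groups drop out of the question:
- Subjects who stop for lack of efficacy or worsening psoriasis, or who start a prohibited therapy, are nonresponders from that date under SAP 5.1.3.2, whatever was measured.
- Subjects lost to follow-up, or who die, have no exit score to file.

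This leaves subjects who withdraw at an unscheduled visit, are not treatment failures, and agree to a PASI and IGA.

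**2. What the text implies for that group.** Footnote b and Protocol 10.2 list procedures to perform; neither renames the visit. Footnote b describes these subjects as leaving before Week 48. SAP 5.2.4 treats not returning at Week 48 as nonresponse. Sensitivity Analysis 3 treats not returning at any visit as missing, without imputation. SAP 5.1.3.3 covers all efficacy analyses and names Week 48 as a key visit. Sensitivity Analysis 2 fills intermittent gaps first and then uses a monotone regression for the rest, a design that expects dropouts to have a missing tail. With a last dose at Week 16 and a final visit at Week 28, Weeks 32 to 48 form that tail. Only a Week 48 label would turn Weeks 32, 36, 40 and 44 into intermittent gaps. All of this points to the same reading: no evaluation at Week 48 means Week 48 is missing.

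**3. The plan's own figure.** SAP Table 1 gives 92% power for PASI 90 at 60% v 70% with 520 per arm. The pooled-variance normal approximation gives 92.3%, so the figure reproduces. It does not depend on how exit visits are labelled.

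**4. Size if every exit score were filed as Week 48.** Let q be the share of an arm that exits early, is not a treatment failure and has an exit score. Let r be the share of those responding at exit. The arm's rate rises by q × r, and the treatment difference shifts by

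(q × r, guselkumab) − (q × r, secukinumab).

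The documents give neither q nor r. Assume q from 2% to 10% (520 × 0.02 ≈ 10 to 520 × 0.10 = 52 subjects per arm) and r from 30% to 70%, the same in both arms:
- Equal q: shift 0.
- q of 2% v 5%: 0.03 × 0.30 = 0.9 to 0.03 × 0.70 = 2.1 points.
- q of 5% v 10%: 0.05 × 0.30 = 1.5 to 0.05 × 0.70 = 3.5 points.

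The sign follows whichever arm loses more subjects. If q is equal at 5% but r is 70% v 50%, the shift is 0.05 × 0.20 = 1.0 point. For scale, the 95% CI half-width at 60% v 70% is 1.96 × √(0.24/520 + 0.21/520) = 5.8 points.

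**The case for a change.** The strongest argument for changing the plan is that the label is nowhere stated and one sentence would state it. Two programmers could in principle handle an exit score differently in confirmatory tests. The phrase in SAP 5.2.4 about returning at Week 48 can be read as calendar time or as the nominal visit, and the second reading would let an exit score into the primary endpoint as well. The per protocol set drops most of these subjects because they missed scheduled doses, but the full analysis set is the main one.

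The silence is real, and that part stands. It does not show that the plan gives a wrong result. Harm requires a labelling choice that no passage directs and that the handling of non-return elsewhere in the SAP speaks against. Nominal labels would ordinarily be set at data capture, in eCRF guidance and dataset specifications outside these documents, and the plan keeps the sponsor blinded until the Week 56 lock.

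Translating the shifts above into lost power or a higher false-positive rate would claim too much. The exit shares are invented. A stand-alone error rate for PASI 100 superiority would also ignore the fixed sequence, in which that test is reached only after primary non-inferiority and superiority and the three earlier major secondary analyses succeed.

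**Conclusion.** No change is needed. This is a missing detail that analysts fill sensibly: an assessment at an exit before Week 48 keeps its own scheduled week or an early-termination label, and Week 48 is missing. The subject is then a nonresponder in the main analyses and is handled as missing in the sensitivity analyses. On that reading the effect on the Week 48 results is zero and no stated power figure moves.

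The unresolved group is small by construction: unscheduled withdrawals who are not treatment failures and who have an exit score. The Week 12 endpoints are untouched, except through the Week 48 half of the combined PASI 75 endpoint. The 0 to 3.5 point range applies only if all exit scores were filed as Week 48 and the assumed exit shares and response rates held. The conclusion rests on ordinary visit labelling at data capture, which the two documents do not show but nothing in them contradicts.
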